All sites in the PFDN are teaching institutions and have accredited fellowship programs in Female Pelvic Medicine and Reconstructive Surgery. Residents and fellows may assist with surgery for ASPIRe participants, similar to standard institutional practices. The certified surgeon is always the surgeon of record for the study and takes full responsibility for the performance and the quality of the procedure. The certified surgeon will be scrubbed in and will perform (or provide hands-on supervision) of the procedure. The certified surgeon assumes full responsibility for assuring proper surgical technique and study standardization of the apical procedures.

J.2. Description of Surgical Interventions

J.2.a. Sacral Colpopexy

The technique for SC needs to be performed in similar fashion when performed by open, laparoscopic, and robotic approach. Vesicovaginal and rectovaginal dissection will be performed in the usual fashion to allow placement of anterior and posterior vaginal mesh arms.

1. Mesh:

- a. Standardize mesh characteristics: knitted, large pore (≥ 1800 microns), light weight (≤ 42 g/m2), high porosity (≥ 60%) monofilament polypropylene mesh (no greater than GyneMesh™) will be allowed. See table for comparison. The specific mesh product will be tracked in data forms.
- b. Y-mesh or two separate arms will be allowed. The two arms may be attached using suture per surgeon's choice.
- c. No xenograft or allograft products.
- No collagen coated mesh.
- e. Mesh type and configuration will be tracked.
- f. The length of the anterior, posterior, and sacral arms implanted will be recorded in the surgeon's report form.
- g. No minimum mesh length is required and is at surgeon's discretion.
- 2. The mesh will be attached with a minimum of 4 attachment sites on each arm (anterior and posterior; 8 total). Additional attachment points are allowed as needed, per surgeon's discretion and usual practice. No self-locking sutures will be allowed.
 - a. Standard suture: While suture types vary across sites, the protocol has standardized the suture type to minimize potential for suture exposure and erosion. Delayed (maxon/pds) or Permanent (prolene/surgipro) monofilament absorbable suture will be used for attachment of mesh to the vagina.
 - b. A minimum size of 2-0 suture is required (0 or 2-0). Given the reports of increased suture erosion, Gortex and braided permanent (Ethibond) suture will not be allowed for vaginal attachment.

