- 5. Anterior and posterior colporrhaphies will be performed at the discretion of the operating surgeon such that points Aa, Ba, Ap and Bp are less than or equal to -1 cm at the end of the procedure (i.e. anterior and posterior vaginal points located at least 1 cm above the hymen) at the end of the procedure. Colporrhaphies, when performed, will be performed with 2-0 or 0 delayed absorbable sutures.
- 6. Surgery for stress urinary incontinence: Stress continence outcomes are not a primary outcome in this study and it is recognized that there is evidence to support universal or selective use of mid-urethral slings in the setting of open sacral colpopexy and vaginal operations for prolapse. Therefore, concomitant full-length transobturator or retropublic mid-urethral slings will be allowed per the discretion of the surgeon. The placement of a mid-urethral sling should not have an effect on the primary outcome because tensionfree vaginal tape has been shown to not provide additional distal anterior vaginal wall support for patients undergoing total mesh colpopexy or laparoscopic colpopexy. [48] The use of retropubic urethropexy at the time of open sacral colpopexy has been described in women without stress urinary incontinence to lessen the risk of postoperative stress urinary incontinence; however, an association of increased anatomic POP failures with those participates who underwent a retropubic urethropexy was identified in this trial. [17] Given the association with retropubic urethropexy with worsening anatomic support and that midurethral slings have not been associated with worsening or improved anatomic support, mid-urethral slings either full-length transobturator or retropubic mid-urethral will be used across all three study groups.

K. OUTCOME VISITS

Outcome visits will occur every 6 months up to a maximum of 60 months. At each of these visits, instruments assessing the primary and secondary outcomes will be administered and a physical exam will be performed to assess anatomic (POP-Q) results, to evaluate for mesh exposures and erosions, and to ask about bulge symptoms (PFDI-Q3) and retreatment so that the primary outcome and safety measures will be assessed. At 6, 12, 24, 36, 48, and 60 months secondary outcome measures will be administered. All women will continue to be

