				0 = No, else if subject attended at least one post-operative visit 6 weeks or after and complication(s) of interest specified above are reported as "Not Evident" across all attended post-operative visits. Subjects with missing responses are included as long as the subject has at least one "Not Evident" response (assuming low missing response rate among attended visits).
Indicator of prolapse mesh exposure in the apex of vagina	CRF-8, CRF- 10/12, AE log	Binary	Post-surgery through last visit	
 
Missing, otherwise
 
Through the timepoint of follow-up, the indicator is defined as follows:
 
1 = Yes, if mesh exposure in vagina is reported as evident (i.e. response of "AE", "SAE") and apex=Yes and Description of Management of Mesh Exposure indicates the mesh was "from/for Prolapse Surgery" (case insensitive) on any of the complication tables as described above
 

				0 = No, else if subject attended at least one post-operative visit 6 weeks or after and complication(s) of interest specified above are reported as "Not Evident" across all attended post-operative visits. Subjects with missing responses are

				<pre>included as long as the subject has at least one "Not Evident" response (assuming low missing response rate among attended visits).</pre> . = Missing, otherwise
Indicator of prolapse mesh erosion (exposure into adjacent organs)	CRF-8, CRF- 10/12, AE log	Binary	Post-surgery through last visit	Through the timepoint of follow-up among subjects who received the hysteropexy surgical intervention as reported on the surgeon's report CRF-8 (i.e. response to question A8 is "Uphold Lite"), based on the systematic collection of open-ended adverse events as reported on the AE log with an onset start date on or after the date of surgical intervention and based on the specific complications as reported on the evaluator (blinded) follow-up CRF-10/12 collected at 6-weeks and in 6-month intervals through 5 years, the indicator is defined as follows:
				1 = Yes, if mesh erosion into viscera (urethra, bladder, ureter, rectum, or bowel locations) is reported as evident (i.e. response of "AE", "SAE") on any of the complication tables as described above

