Indicator of midurethral sling (MUS)mesh exposure in the distal (lower half/introitus) vagina	CRF-8, CRF- 10/12, AE log	Binary	Post-surgery through last visit	Through the timepoint of follow-up, the indicator is defined as follows: 1 = Yes, if mesh exposure in vagina is reported as evident (i.e. response of "AE", "SAE") and distal (lower half/introitus)=Yes and Description of Management of Mesh Exposure indicates the mesh was "from/for sling" (case insensitive)

				on any of the complication tables as described above 0 = No, else if subject attended at least one post-operative visit 6 weeks or after and complication(s) of interest specified above are reported as "Not Evident" across all attended post-operative visits. Subjects with missing responses are
				included as long as the subject has at least one "Not Evident" response (assuming low missing response rate among attended visits).
				. = Missing, otherwise
Indicator of midurethral sling	CRF-8,	Binary	Post-surgery	Through the timepoint of follow-up, the indicator is defined as follows:
(MUS)mesh exposure in the apex of vagina	CRF- 10/12, AE log		through last visit	1 = Yes, if mesh exposure in vagina is reported as evident (i.e. response of "AE", "SAE") and apex=Yes and Description of Management of Mesh Exposure indicates the mesh was "from/for sling" (case insensitive)
				on any of the complication tables as described above
				0 = No, else if subject attended at least one post-operative visit 6 weeks or after and complication(s) of interest specified above are reported as "Not Evident" across all attended post-operative visits. Subjects with missing responses are included as long as the subject has at least one "Not Evident" response (assuming low missing response rate among attended visits).
				. = Missing, otherwise
Indicator of midurethral sling (MUS) mesh erosion (exposure into adjacent organs)	CRF-8, CRF- 10/12, AE log	Binary	Post-surgery through last visit	Through the timepoint of follow-up among subjects who received transobturator or retropubic midurethral sling as reported on the surgeon's report CRF-8 (i.e. questions E1 or E2 is "Yes" for performed), based on the systematic collection of open-ended adverse events as reported on the AE log with an onset start date on or after the date of surgical intervention and based on the specific complications as reported on the evaluator

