				(blinded) follow-up CRF-10/12 collected at 6-weeks and in 6-month intervals through 5 years, the indicator is defined as follows:
				1 = Yes, if mesh erosion into viscera (other specified location containing "sling") is reported as evident (i.e. response of "AE", "SAE") on any of the complication tables as described above or on the AE log identified by the AE verbatim term containing "mus mesh erosion" (case insensitive)
				If subject did NOT receive hysteropexy surgical intervention as reported on the surgeon's report CRF-8 (i.e. response to question A8 is "Uphold Lite"), then mesh erosion into viscera (urethra, bladder, ureter, rectum, bowel, or other specified locations) reported as evident (i.e. response of "AE", "SAE") on any of the complication tables as described above are also included as there are no other sources of mesh.
				0 = No, else if subject attended at least one post-operative visit 6 weeks or after and complication(s) of interest specified above are reported as "Not Evident" across all attended post-operative visits. Subjects with missing responses are included as long as the subject has at least one "Not Evident" response (assuming low missing response rate among attended visits).
				. = Missing, otherwise
				*Note: See above masked review note specified for outcome Indicator of hysteropexy mesh exposure.
Change from baseline in surgical pain scale SPS rest subscale score**	SPS	Continuous	6-weeks thru last visit	The SPS rest subscale score will be computed at baseline and at each timepoint's corresponding attended post-operative visit during which assessments are administered and collected using standard scoring algorithms (Barber 2012). Specifically, score the response for question Q1 (0=no pain sensation,, 10=most intense pain imaginable). If the

				question is missing a response, then the score is not calculated. The outcome will then be computed as the difference in score at each timepoint's corresponding attended post-operative visit and the score at baseline. If data for the assessment are missing at a timepoint's corresponding attended post-operative visit, the outcome variable will be coded as missing.

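### SAP 10.2 cannot count a visceral erosion of sacral colpopexy mesh as prolapse-mesh erosion, and books it to the sling when the woman had a study sling

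*SAP*

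**What the plan says.** **Prolapse-mesh erosion (SAP 10.2).** The indicator is evaluated "Through the timepoint of follow-up among subjects who received the hysteropexy surgical intervention as reported on the" surgeon's report, with the qualifying answer given as Uphold Lite to question A8 of CRF-8. Within that set, an erosion into the urethra, bladder, ureter, rectum or bowel marked evident on a complication table counts as an event. The rule has no condition on which mesh eroded.

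**Sling-mesh erosion (SAP 10.2).** The indicator is evaluated "among subjects who received transobturator or retropubic midurethral sling as reported on the" surgeon's report (CRF-8 E1 or E2 performed). It counts "mesh erosion into viscera (other specified location" whose text contains the word sling, or a matching verbatim term on the AE log. It then adds a default, opening "If subject did NOT receive hysteropexy surgical intervention as reported on the" surgeon's report: in those women visceral erosions at the listed organs or another specified location "are also included as there are no other sources of mesh".

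**Which arms carry mesh.** Protocol J.2.a describes dissection in sacral colpopexy to "allow placement of anterior and posterior vaginal mesh arms". Protocol J.5 says "mid-urethral slings either full-length transobturator or retropubic mid-urethral will be used across all three study groups", at the surgeon's discretion.

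**What the rows are for.** SAP 3.1.2 lists comparison of mesh erosion and exposure across the three methods as a safety aim, and SAP 3.2 names erosion into another organ as part of the mesh-complication outcome.

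**Source labelling.** SAP 7.5 requires queries before lock so that every exposure or erosion is labelled as coming from prolapse surgery or from a sling. The vaginal exposure rows of SAP 10.2 test for that source and have no Uphold LITE restriction.

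**The concern.** The prolapse-mesh row recognises one prolapse mesh, while the trial uses two. Protocol Appendix B, section 3.4, itself places potential mesh complications in two of the three arms. The sling default rests on a factual premise, that a woman without Uphold LITE has no mesh other than her sling, and SC contradicts it.

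The row on which TVM mesh and SC mesh would be compared for visceral erosion therefore covers only one of them, and the sling row can hold erosions that are not from slings. In a trial prompted largely by questions about mesh safety, a reader will look to these rows for that comparison.

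The wording may have been carried over from a trial with a single prolapse-mesh arm; this is inference. Hysteropexy cannot occur in women who must already have had a total hysterectomy. The sling row also carries the instruction "See above masked review note specified for outcome Indicator of hysteropexy mesh exposure", and no row of that name appears in SAP 10.2 as supplied (the extracted table is damaged in places). No reason is given for leaving SC out.

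**Working it through.** The plan has no figure to reproduce here. The check applies each rule as written to a visceral erosion marked evident on a complication table at one of the listed organs.

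**Inputs**
- Prolapse row: evaluated if A8 is Uphold Lite; event if a listed organ is marked (SAP 10.2).
- Sling row: evaluated if E1 or E2 was performed; event if the specified location contains the word sling, or the AE log term matches, or the woman has no Uphold LITE and a visceral site is marked (SAP 10.2).
- SC mesh implanted: Protocol J.2.a. Slings possible in every arm: Protocol J.5.

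**Trace**

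| Surgery received | Study sling | True source | Prolapse row | Sling row | Correct? |
|---|---|---|---|---|---|
| SC | yes | SC mesh | outside set | 1 | no |
| SC | no | SC mesh | outside set | outside set | no |
| SC | yes | sling | outside set | 1 | yes |
| TVM | yes | Uphold LITE | 1 | 0 | yes |
| TVM | no | Uphold LITE | 1 | outside set | yes |
| Native tissue | yes | sling | outside set | 1 | yes |

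The first line gives the same result for bladder, rectum and bowel, and does so even when the record is labelled as prolapse surgery, because the default does not consult the label. The first and third lines are indistinguishable in the output: among SC women with a sling, the sling row cannot tell the two meshes apart.

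**Size.** Let N be the number of visceral erosions of SC mesh so recorded, and s the share of those women with a study sling.
- Counted in the prolapse row: 0
- Counted in the sling row: N × s
- Counted in neither row: N × (1 − s)
- Total misplaced: N × s + N × (1 − s) = N, for any s from 0 to 1

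As an assumed illustration, N = 2 and s = 0.5 gives 2 × 0.5 = 1 booked to the sling and 2 × 0.5 = 1 in neither row. Against the planned 121 per arm, 1, 2 or 3 such events would be 1/121 = 0.8%, 2/121 = 1.7% or 3/121 = 2.5% of SC women. These counts are assumptions. The documents give no visceral erosion rate for SC mesh and no expected share with slings.

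**Later changes.** SAP Section 12 (Version 2) clarifies the proportional-hazards test and adds a post-hoc sensitivity analysis. It changes neither erosion rule.

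**The case against.** **The source label already solves this.** In part. If the SAP 7.5 label sits in the specify-location field, the first branch of the sling rule could read it, since that branch searches for the word sling. It would go too far to say that neither rule can use the label. But the prolapse row has no source test, and the sling default applies whatever the label says, so an SC erosion correctly labelled as prolapse surgery is still booked to the sling.

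**The SC column need not be empty.** This stands. SAP Section 5 displays a woman who switched procedure after an intraoperative complication or contraindication under her randomized surgery, while SAP 10.1 refers to treatment received. A woman randomized to SC who received Uphold LITE could therefore appear in the SC column. Her event would not be an erosion of SC mesh.

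**The gap would be noticed.** Also fair. Women who had only SC are outside the evaluated set, so the literal output is not evaluated, not a false 0%. The quieter error is the one in SC women with a study sling.

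**The consequence is limited.** Secondary p-values and intervals are descriptive (SAP 7.7). Reportable events remain in the AE and SAE tables, and complications remain in the Dindo scores. All of this stands, but the SAP does not define those displays by mesh source, so they do not replace the comparison that the erosion row was meant to give.

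**Conclusion.** The defect is certain on the text and narrow in reach. No visceral erosion of SC mesh can be counted as prolapse-mesh erosion. It is counted as sling erosion when the woman had a study sling, and is in neither erosion row when she did not. All N such events are misplaced for any sling share; N is unknown and may be small. The trace assumes that the event is recorded on the complication tables at a listed organ and that the woman did not receive Uphold LITE.

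Four stronger readings are tempting, and the documents do not support them:
- That the SC column will be empty or will show 0%. Switchers may appear there, and women with SC alone are not evaluated.
- That SC erosions vanish from safety reporting. The AE, SAE and Dindo displays are untouched.
- That the SC erosion rates cited in Protocol Section B give the number affected. They do not separate vaginal from visceral erosion.
- That sling erosions in TVM women are wrongly booked to Uphold LITE. That happens only if they are entered under a listed organ without the word sling, and the documents do not show how they are entered.

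The vaginal exposure rows and the primary outcome are unaffected. The point should be fixed because erosion is a named safety outcome compared across the three methods and the remedy is cheap.

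**What to change.** 1. Evaluate prolapse-mesh erosion in all women who received prolapse mesh, whether Uphold LITE or SC.
2. In every arm, attribute each visceral erosion by the prolapse-surgery or sling label queried under SAP 7.5. Confirm first which field holds that label for visceral erosions, since the SAP does not say.
3. Limit the default that assumes no other mesh to sling recipients with neither Uphold LITE nor SC mesh.
4. Date the change. SAP Version 2 already reports failure events by arm, so a change made after it should be disclosed as a post-unmasking correction.

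The cost is SAP wording and two derivations. The source label is already queried before lock, and Protocol J.2.a has the SC mesh product recorded on the data forms. No clinical procedure changes, and no new data collection is needed if the label field is confirmed.
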